Extracorporeal shockwave therapy (ESWT or SWT) is a process in which energy is delivered to the muscles or tendons for pain relief.⁷ A recent network meta-analysis showed that ESWT is effective in treating AT when combined with ECC.¹ Moreover, a recent narrative review presented ESWT as an effective treatment for specific tendinopathies, including AT.⁸ Notably PBMT was not able to be compared in the analysis due to no published studies meeting criteria for inclusion. There is also limited information available on the best energy settings to be used in treating AT and the impacts on short term recovery;¹ therefore more research needs to be done into the impact of ESWT on treating AT.

Photobiomodulation therapy (PBMT) and ESWT are effective tendinopathy treatments, and a study on the treatment of other tendons in the body - lateral epicondylitis (tennis elbow) - showed improvement in both the PBMT and the ESWT arms, with ESWT showing a significant difference in increasing handgrip strength.⁹ Studies such as this are promising that ESWT and PBMT will be effective in treating other tendon injuries such as AT, however, these treatment methods have not been evaluated in comparison or combination with each other. Promising results from these studies combined with the previous unclarity in the best treatment for AT justifies the need for more research.

This combination of treatment (SWT + PBMT) may provide improved healing over siloed modalities. ESWT works by creating microtears that in turn stimulate the body's inflammatory response and healing cascade.⁷ PBMT could then increase this cascade further by increasing the cellular function, particularly when the body is in an inflamed state, such as the state after ESWT.^{2,6} Thus, this treatment combination should be explored.

The sub-section of AT amongst Active-Duty (AD) personnel has had very limited research and given the high prevalence, should be addressed. Therefore, our study will compare four different treatment arms utilizing traditional physical therapy (PT), PT plus shockwave therapy (SWT), PT plus PBMT, and PT plus SWT and PBMT. Both self-reported questionnaires and measured outcomes will be used to assess the most effective treatment for AT.

9.3

Objectives/Specific Aims/Research Questions:

Describe the purpose and objective(s) of the study, specific aims, and/or research questions /hypotheses

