PT + Shockwave Therapy (SWT) Arm:

The *physical therapy + shockwave therapy* arm will receive SWT once a week for three weeks in addition to the PT treatment described above. Twice a week, for three weeks, a team member will check-in with the participants to ensure physical therapy exercise adherence, and response to treatment. During the second check-in of the week, the study team member will also ensure the participant is keeping their activity/medication/pain log; the study team member will also deliver the DVPRS with supplemental questions. (See Appendix F for Check-in Data Collection CRF). The first check-in of the week will occur in-person after the SWT, if, however, this is not feasible, it may be conducted virtually; the second check-in of the week may occur virtually or in-person.

In total, participants will receive one SWT treatment each week (in person) and complete two check-ins each week (remote or in person), for three weeks. The SWT will take approximately 5-20 minutes.

A medical provider will conduct SWT on study participants, using the OrthoPlus Ultra 100 /radial D-Actor. (See OrthoPulse Radial Edition Application Brochure and OrthoPlus Ultra 100 Operations Manual). This Extracorporeal Pressure Activation Treatment (EPAT) device will be used at a radial shockwave of 3000 counts treatment settings of 15 Hz minimum 2 bars with a focus applicator head at mid-portion of Achilles using clinical focusing technique, and 3000 counts at 15 Hz minimum 2.5 bars using broad oscillator to myotendinous region and over symptomatic areas of gastrocnemius and soleus, treatment will be applied distally to proximally to facilitate lymphatic return adjusting treatment air pressure and amount of force applied by applicator head by patient comfort. The maximum setting for each treatment applicator will be 4 bars of air pressure, and the first 500 counts using each applicator will be applied at 1.5 bars to help desensitize the tissue prior to increasing energy settings. The settings used for each participant will be recorded and followed in a similar approach to treatment.

A CuraMedix representative will provide training to the study team for this machine.

In Part 1, participants in this group will have 8 visits: 3 combined SWT and check-ins post-treatment (in person), 3 check-in only visits (remote or in person), 6-week follow-up (virtual or in-person), and 3 month follow-up (in person).

PT + Photobiomodulation Therapy (PBMT) Arm:

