The *physical therapy + photobiomodulation therapy* arm will receive PBMT twice a week, for three weeks, in addition to the PT treatment described above.

A member of the study team will measure the treatment area according to a standard protocol (Appendix N PBM Dose Calculations), to calculate and determine the treatment time, approximately 5-20 minutes. PBMT will be delivered at 25W.

The PBMT will be provided by a trained study team member. Training for the PBMT will be conducted by a LightForce representative. PBMT will be delivered using the LightForce® XPi 25W device with the Smart Hand Piece technology, provided by LiteCure, LLC/DJO (New Castle, DE) which has a built-in accelerometer in the hand piece that controls the speed of light delivery to the treatment area. The LightForce® XPi therapy laser is an FDA cleared device for the treatment of pain. The trained team members will use the Smart Hand Piece technology, which achieves effective treatments and improves dosing accuracy by assessing the operator's speed and providing real-time visual (red – amber – green light) and sensory feedback. The Smart Hand Piece is calibrated to shut-off when moving too slowly, and warn the operator when moving too fast by vibrating. (See LightForce Brochure). The therapy is delivered through a flexible optical fiber threaded through the hand piece, which contains a rolling glass massage ball. PBMT will be delivered at 10 J/cm² and applied in a serpentine pattern to the calf from the fold in the back of the knee to the bottom of the leg including distal Achilles tendon and calcaneus. The setting for treatment will be adjusted for skin pigmentation using the Fitzpatrick Scale and values recorded for each participant.

After each PBMT visit (twice a week, for three weeks), a team member will check-in with the participants to ensure physical therapy exercise adherence, and response to treatment. During the second check-in of the week, the study team member will also ensure the participant is keeping their activity/medication/pain log; the study team member will also deliver the DVPRS with supplemental questions. When/if needed, check-ins may occur virtually. (See Appendix F for Check-in Data Collection CRF).

In Part 1, participants will receive PBMT twice each week, for three weeks. The PBMT treatment arm requires 8 visits: 6 combined PBMT and check-ins (in person), 6-week follow-up (virtual or in-person), and 3-month follow-up (in person).

PT + SWT and PBMT Arm

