The *physical therapy + shockwave therapy + photobiomodulation therapy* arm will receive both SWT and PBMT treatments in addition to PT treatment described above. The SWT and PBMT will be performed by a trained study team member. Participants will receive PBMT twice each week and SWT one time each week, for three weeks. The SWT visit may be combined with a PBMT visit in the same week. Up to two times each week after a treatment visit (for three weeks), a team member will check-in with the participants to ensure physical therapy exercise adherence, and response to treatment. During the second check-in of the week, the study team member will also ensure the participant is keeping their activity/medication/pain log; the study team member will also deliver the DVPRS with supplemental questions. When /if needed, these check-ins may occur virtually. (See Appendix F for check-in data collection CRF).

In Part 1, the PT+ SWT + PBMT treatment arm requires 8 visits: 3 for PBMT alone with check-ins (in person), 3 for PBMT & SWT with check-ins (in person), 6-week follow-up (virtual or in-person), and 3-month follow-up (in person).

Part 2

At the 3-month follow-up, participants who are not satisfied with their current treatment response will be given the option to choose any one of the remaining treatment arms. Participants will also have the option to decline further treatment. Any biological female of child bearing age and capacity that opts to receive treatment with SWT and/or PBMT will be required to complete a urine hCG test prior to receiving treatment in Part 2 of the study.

For all groups in Part 2, the number of non-PT study treatment visits the participants will need to complete will be dependent on which treatment arm the participant selects; however, regardless of what treatment the participant chooses, if any, the participant will be required to complete at least one in-person visit at the 6-month follow-up.

Follow-Up Data Collection:

Regardless of study arm assignment, all participants will be asked to log their activity, pain, and medication intake (Appendix E), daily for 12 weeks. This log will be collected/checked weekly for the first 3 weeks and then at the 6-week and 3-month follow-up visits.

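### Weekly pain scores in weeks 1-3 follow a device visit in two arms and not in the other two, and the combination arm fixes neither the SWT visit nor the device order

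*Combined protocol and SAP*

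**What the plan says.** All arm descriptions are in section 10.1, Part 1. Every arm has two check-ins a week for three weeks (the combination arm says up to two), and the DVPRS with its supplemental questions is given at the second.

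- **PT only arm.** Check-ins may be virtual or in person, and no device is used.
- **PT + SWT arm.** SWT is tied to the start of the week: "The first check-in of the week will occur in-person after the SWT", unless that is not feasible. The visit list adds "3 check-in only visits (remote or in person"), so the second contact of the week carries no device.
- **PT + PBMT arm.** "After each PBMT visit (twice a week, for three weeks), a team member will check-in with the participants". Both weekly contacts are therefore treatment visits, and the check-in comes after treatment.
- **PT + SWT and PBMT arm.** PBMT is given twice and SWT once a week. On placement the text says only "The SWT visit may be combined with a PBMT visit in the same week". On check-ins it says "Up to two times each week after a treatment visit (for three weeks), a team member will check-in". The visit list is "3 for PBMT alone with check-ins (in person), 3 for PBMT & SWT with check-ins (in person"). Neither the order of the two visit types within a week nor the order of devices within a combined visit is stated.

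Section 9.2 justifies the combination by suggesting that PBMT could add to the healing response, "particularly when the body is in an inflamed state, such as the state after ESWT". Section 14.1 expects a pain response to SWT.

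Section 10.1, Follow-Up Data Collection, makes the supplemented DVPRS weekly for three weeks, whereas the DVPRS entry in section 10.2 has the supplemental part given at every visit.

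**The concern.** Two linked matters are left loose.

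The first is when pain is measured. A score taken just after a device session may reflect the session as well as the tendon. SWT is expected to provoke pain, and the laser is described in section 10.1 as cleared for treating pain, so a score taken after either could move for reasons unrelated to lasting benefit. If two arms are scored after a device and two are not, a between-arm difference in weeks 1 to 3 mixes treatment effect with measurement timing. The combination arm adds a further difference, because its score may also fall at the SWT visit while the SWT arm's score does not.

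The second is what the combination consists of. Participants in that arm can receive the devices in different orders and at different points in the week, all within protocol. A PBMT-first visit fits the reasoning in section 9.2 less well than an SWT-first visit. The SWT settings are recorded ("The settings used for each participant will be recorded and followed in a similar approach to treatment"), but the section does not ask for device order, so the variation might not be recoverable afterwards.

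At stake are the interpretation of early pain trends and the uniformity of one arm's treatment.

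**Working it through.** The plan states no figure on this point. The check sets the arm descriptions side by side and counts what they allow.

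**Inputs.** 40 participants per arm (sections 11.2 and 11.4); one DVPRS a week for three weeks, at the second check-in (section 10.1). Assumptions: the weekly schedule applies, all check-ins are in person, two take place each week, and nobody is lost.

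**Number of scores.** 3 × 40 = 120 per arm; 120 × 4 = 480 in all.

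**Timing of those scores by arm.**

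| Arm | Second weekly contact | After PBMT | At an SWT visit |
|---|---|---|---|
| PT | check-in, no device | 0 of 120 | 0 of 120 |
| PT + SWT | check-in, no device | 0 of 120 | 0 of 120 |
| PT + PBMT | PBMT, then check-in | 120 of 120 | 0 of 120 |
| PT + SWT + PBMT | PBMT, with or without SWT, then check-in | 120 of 120 | 0 to 120 of 120 |

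The PBMT column follows from a stated rule: in both PBMT-containing arms the check-in comes after a treatment visit, and each of those visits includes PBMT. Thus 240 of 480 scores follow a device, all in two arms. The SWT range in the last row comes from the open choice of visit. With 28 per arm, the planned final sample, the per-arm maximum is 3 × 28 = 84 and the pattern is unchanged.

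**Schedules open to the combination arm.** The list of 8 visits (3 + 3 + 2 follow-ups) implies that SWT shares a PBMT visit; separate SWT visits would make 6 + 3 + 2 = 11. With combined visits there are two choices, which visit and which device first. Using the same pattern every week (S = SWT, P = PBMT, D = DVPRS, bar = between visits):

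| Schedule | Week | D at an SWT visit | P after S, same visit | S followed by any later P | P before any S |
|---|---|---|---|---|---|
| Visit 1, SWT first | S P \| P D | 0 of 3 | 3 of 3 | 3 of 3 | 0 of 6 |
| Visit 1, PBMT first | P S \| P D | 0 of 3 | 0 of 3 | 3 of 3 | 1 of 6 |
| Visit 2, SWT first | P \| S P D | 3 of 3 | 3 of 3 | 3 of 3 | 1 of 6 |
| Visit 2, PBMT first | P \| P S D | 3 of 3 | 0 of 3 | 2 of 3 | 2 of 6 |

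Two of the four schedules put the score at the SWT visit, and two give PBMT before SWT at the combined visit. Only the first row does neither. In three of four, every SWT session is followed by some PBMT session; in the fourth, two of three are, because the next week's first visit supplies it.

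**If the DVPRS is taken at every visit (section 10.2).** There are six contacts in weeks 1 to 3. The SWT arm has 3 SWT visits and 3 check-ins only; the combination arm has 3 combined visits and 3 with PBMT alone. So 3 of 6 scores per participant fall at an SWT visit in both arms. The SWT counts then match and only their place in the week can differ. The PBMT imbalance remains: 6 of 6 contacts in the two PBMT-containing arms and none in the others.

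**The case against.** The best defence is that little depends on these scores. The analyses in sections 11.1 and 11.6 concern change at 3 months, with VISA-A as the primary measure. The weekly DVPRS is not named there; that it would enter the longitudinal sensitivity models is an inference from its place among the outcomes in section 10.2. The daily pain log and the 3- and 6-week self-report batteries also capture early symptoms. All of this stands and keeps the point minor.

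Second, check-ins may be virtual in every arm. A virtual second check-in need not come straight after a device, so the counts above are maxima. This stands. It reduces the imbalance by an unknown amount but does not remove it, since the PBMT and combination visit lists show in-person check-ins as the norm.

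Third, a reader might infer that PBMT before SWT contradicts the plan's own rationale. It does not. Section 9.2 is hedged, sets no interval and does not require both devices in one session; most permitted schedules still give PBMT after every SWT. All that can be said is that some orders fit the rationale less well than others.

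Fourth, a reader might infer from section 14.1 that SWT pain inflates the DVPRS. That section concerns keeping pain tolerable while SWT is being given; it does not say that the pain persists into a later score. Neither the size nor the direction of any shift can be taken from the documents.

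Finally, the check-in form, flow diagram and data collection schedule (Appendices F, L and T) are cited but were not in the text reviewed. They may fix visit order or score timing. If so, section 10.1 should say the same.

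**Conclusion.** The point holds as a minor one. By the arm descriptions themselves, the weekly DVPRS in weeks 1 to 3 follows a device visit in the PBMT and combination arms and a contact without a device in the PT and SWT arms. With in-person check-ins the contrast is up to 240 of 240 scores against 0 of 240. In the combination arm, 0 to 120 of 120 may also fall at an SWT visit, because neither the visit nor the device order is fixed; the SWT arm has none. Early pain scores are therefore not comparable in timing across arms, and delivery of the combination can vary within protocol.

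This rests on the weekly schedule, in-person check-ins, full attendance and 40 per arm, and on nothing in the unseen appendices overriding section 10.1. A reader might go on to infer bias in the primary result. The documents do not support that: the 3-month VISA-A comparison is made long after the three treatment weeks and does not use these scores. No effect on any estimate is claimed.

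**What to change.** 1. In the combination arm of section 10.1, replace the permissive sentence on visit sharing with: *SWT will be given at the first PBMT visit of each week, with PBMT immediately after it; the second weekly visit is PBMT alone.*
2. In the PBMT and combination arms, collect the weekly DVPRS before treatment at the second weekly visit, including when the check-in itself is held virtually.
3. Record the device order at each combined visit.
4. Align the DVPRS entry in section 10.2 with the weekly schedule. If a score at every visit is intended, require collection before treatment at every device visit, including those in the SWT arm; otherwise first-visit scores will still follow a device.

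Under the weekly schedule, 0 of 480 scores then directly follow a device, SWT falls at the week's first contact in both SWT-containing arms, and PBMT follows SWT at 3 of 3 combined visits. The number of days between the two weekly contacts is not fixed in any arm, and this change leaves it so.

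The cost is one replaced sentence, a timing clause in each of two arms, the section 10.2 wording, and a small change to the check-in form. The 8 visits stay at 8. A combined visit takes about 10 to 40 minutes (5 to 20 for each device), but the visit list already assumes combined visits. The combination arm loses a little scheduling flexibility, and a virtual check-in will need its score collected separately at the treatment visit.

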If the potential participant meets eligibility criteria as determined by the Inclusion/Exclusion CRF and expresses interest in participating, an authorized study team member will initiate the formal consent discussion and, if applicable, obtain informed consent.

Pre-screening conversations may also take place remotely, should a participant contact the study team, using the Screening Script (Appendix O). Potential participants who meet initial eligibility per the Screening Script and express interest in participating will be asked to come to clinic to complete an Inclusion/Exclusion CRF to confirm final eligibility with an authorized study team member prior to providing informed consent as outlined in the respective section below.

Participants are enrolled once the consent process is completed.

Baseline Data Collection/Week 1 Visit 1 (post-consent):

Post-consent, secondary exclusion of pregnancy will be determined by a hCG test for women, which will be conducted by the lab, and completed prior to randomization.

Questionnaires: Prior to receiving their assigned study treatment, participants will provide their contact information (Appendix B Intake CRF) and complete demographic (Appendix C Demographics CRF) and study specific measures (Appendix D Baseline Data Collection CRF).

Ultrasound: A study team member will assess ultrasound measures at baseline for both limbs. Measures of interest include cross-sectional area, width and degree of thickening within the tendon at site of maximal circumference and maximal pain, relative neovascularity, and elastography. A trained study team member will conduct the ultrasound.

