Check-ins (remote or in person, as applicable/convenient) will be conducted twice a week for the first three weeks. Any issues with treatment will be recorded on Appendix F Weekly Check-In CRF. In addition, once a week, for the first 3 weeks, the DVPRS with supplemental questions will be administered.

A chart review will be completed at 3 months to ensure that all PT visit information is recorded in study documentation (Appendix G). A medical record review will be completed to obtain this information. A study visit is not required on behalf of the participant.

A self-report battery will be obtained for each Achilles tendon, regardless of treatment, using Appendix H Follow-Up Data Collection CRF, which will be administered at 3-weeks, 6-weeks, 3-months, and 6-months post-intervention start.

Participants will complete the ultrasound imaging, heel raise test, ankle strength and ROM, hopping test, and be asked to complete a patient satisfaction and expectation survey at the 3-month and 6-month timepoints.

Participants will be evaluated for adverse events at each follow-up time point and any complications will be documented.

Data may be captured in person or remotely (e.g., entered directly into REDCap using a personalized coded link with no log-in required, verbally over the phone with a study team member, etc.). Reminder phone calls, texts, and/or emails will be sent to participants at their preferred contact method indicated on the Intake Form (Appendix B).

Please see the Study Flow Diagram (Appendix L) for a visual representation of the study procedures.

Missed Appointments and Study Removal:

If a participant misses a scheduled appointment, they will be contacted to reschedule in order to maintain the treatment plan of their assigned study treatment group. In the event that a participant misses an appointment, study staff will make one attempt to reschedule each day on three separate days (for three total attempts to reschedule). If the participant cannot be reached or does not respond/reschedule, they will be removed from the study due to non-compliance.

10.2 Data Collection:

Describe all the data variables, information to be collected, the source of the data, and how the data will be operationally measured.

Questionnaires:

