List the statistical methods to be used to address the primary and secondary objectives, specific aims, and/or research hypotheses. Explain how missing data and outliers will be handled in the analysis. The analysis plan should be consistent with the study objectives. Include any subgroup analyses (e.g., gender or age group). Specify statistical methods and variables for each analysis. Describe how confounding variables will be controlled in the data analysis

Descriptive statistics will report location and scale in terms of mean and standard deviation for normally distributed variables, median and interquartile intervals for ordinal metric variables, and in terms of proportion and size for categorical variables.

Outliers will be removed if determined to be erroneous based on relevant clinical expertise. Data will be analyzed on a complete-case intention-to-treat (ITT) basis. Confounding will be principally controlled by randomization. In order to increase the precision of our estimates, we may also statistically adjust for patient demographics and relevant clinical variables if warranted based on statistical best practices.

Methods to be used for the Primary Aim: Time-to-event analyses (return to activity) will use survival analysis. All other outcome measures (including our primary outcome measure (VISA-A) and other aforementioned secondary outcome measures such as functional testing, ultrasound measures, etc.) will be analyzed using generalized additive models predicting change in each outcome measure by treatment group at 3 months. Sensitivity analyses for non-time-to-event outcome measures will be performed to evaluate trends by treatment group and will use longitudinal hierarchical/multilevel models incorporating random effects to account for repeated measures.

Methods to be used for the Secondary Aim: Due to the lack of washout period between initial and cross-over periods, as well as the removal of patient blinding (patients may choose the specific treatment they wish to receive during this final 3-month period), cross-over response will be analyzed as an exploratory aim versus an inferential aim. Due to the exploratory nature of this aim, additional or adjusted analyses may be performed to best explore and evaluate the data collected. Generalized additive models will be used to explore cross-over results and a limited set of measures will be explored (patient satisfaction, functional tests, ultrasound measures).

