Multilevel models will incorporate random effects to account for repeated measures, using distribution families and link functions appropriate for the outcomes of interest, determined using QQ plots analyzed for best model fit. All statistical analyses will be performed using the R Programming language.

11.2 Sample Size:

We are requesting to enroll 160 total participants (40 per initial treatment arm) after adjusting for screen failures and attrition for a final sample of at least 112 (28 per initial treatment arm). 35 patients in each initial treatment group (140 patients total) will achieve 90% power to detect an effect size of 16 points. 30 patients in each initial treatment group (120 patients total) will achieve 90% power to detect an effect size of 17 points. 25 patients in each initial treatment group (100 patients total) will achieve 90% power to detect an effect size of 18 points. Effect size for the purpose of power calculations was defined as the difference between VISA-A at 3 months between PT only and PT + Additional Treatment (assumptions were based on PT + PBMT due to availability of comparable historical research), with statistical significance defined as $\alpha = 0.05$.

11.3 Total number of subjects requested (including records and specimens):

160

11.4 If you are recruiting by study arm, please identify the arms of the study and how many subjects will be enrolled in each arm

Across all performance sites, up to 160 participants will be randomized 1:1:1:1 to the four initial treatment arms (40 participants per arm)

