11.5 Please provide a justification for your sample size

Power was calculated using repeated Monte Carlo Markov Chain simulations predicting 3-month VISA-A between treatment arms, and sourced assumptions of mean and spread from Tumilty et al (2016). MCID was considered to be a 6.5 point difference in VISA-A¹⁴.

11.6 Data Analysis Plan: Complete description: Background, Objectives, Design, Step by Step how the project is going to be done, Data analysis plan:

Outliers will be removed if determined to be erroneous based on relevant clinical expertise. Data will be analyzed on a complete-case intention-to-treat (ITT) basis. Confounding will be principally controlled by randomization. In order to increase the precision of our estimates, we may also statistically adjust for patient demographics and relevant clinical variables.

Methods to be used for the Primary Aim: Time-to-event analyses (return to activity) will use survival analysis. All other outcome measures (including our primary outcome measure (VISA-A) and other aforementioned secondary outcome measures) will be analyzed using generalized additive models predicting change in each outcome measure by treatment group at 3 months. Sensitivity analyses for non-time-to-event outcome measures will be performed to evaluate trends by treatment group and will use longitudinal hierarchical/multilevel models incorporating random effects to account for repeated measures. Analyses under the primary aim will use the initial 3-month cohort only.

Methods to be used for the Secondary Aim: Due to the lack of washout period between initial and cross-over periods, as well as the removal of patient blinding (patients may choose the specific treatment they wish to receive during this final 3-month period), cross-over response will be analyzed and treated as an exploratory aim versus an inferential aim. Due to the exploratory nature of this aim, additional or adjusted analyses may be performed to best explore and evaluate the data collected. Generalized additive models will be used and a limited set of measures will be explored (patient satisfaction, functional tests, ultrasound measures).

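### Participants removed after a missed visit have no provision for a 3-month VISA-A, so the complete-case primary analysis may be selected on attendance

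*Combined protocol and SAP*

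**What the plan says.** Under Missed Appointments and Study Removal, section 10.1 states that after a missed appointment "study staff will make one attempt to reschedule each day on three separate days", and then: "If the participant cannot be reached or does not respond/reschedule, they will be removed from the study due to non-compliance". The wording is mandatory and can be triggered by a single missed visit.

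Section 13.6, under withdrawal without participant consent, lists failure to adhere to the protocol or therapy plan among grounds on which participation may be stopped, which is discretionary. The statement in 13.6 that collection ceases at withdrawal, and that earlier data may be kept, is written for participants who withdraw themselves.

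On follow-up, section 10.1 schedules the self-report battery at 3 weeks, 6 weeks, 3 months and 6 months, and says "Data may be captured in person or remotely", giving a no-login REDCap link and telephone as examples, with reminders by phone, text or email.

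On analysis, section 11.1 says "Data will be analyzed on a complete-case intention-to-treat (ITT) basis". Primary and most secondary outcomes use "generalized additive models predicting change in each outcome measure by treatment group at 3 months" (11.1 and 11.6). Sensitivity analyses use "longitudinal hierarchical/multilevel models incorporating random effects to account for repeated measures". Section 11.2 plans 160 enrolled "after adjusting for screen failures and attrition for a final sample of at least 112 (28 per initial treatment arm").

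**The concern.** The removal rule follows a sentence about maintaining the assigned treatment plan, which is a treatment aim, yet it takes the person out of the whole study, outcome collection included. Because the primary analysis uses only participants with a 3-month score, the analysed set is partly defined by attendance after randomisation. Complete-case analysis is the declared method, so the rule does not contradict the plan, but it weakens the intention-to-treat label.

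At stake is the comparison of PT alone with PT plus devices on VISA-A. If removal is related to outcome and its frequency differs by arm, the contrast moves. If more participants who are doing badly are removed from a device arm, the device looks better than it is. If more are removed from PT only, it looks worse.

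**Working it through.** **1. The chain in the text.** Missed visit, three attempts, removal (10.1). No later request for VISA-A from that person in the text available for review. No 3-month score, so not a complete case (11.1, 11.6). Each step follows from the one before.

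**2. The plan's own figure on loss (11.2).** 160 − 112 = 48, and 48/160 = 30%; per arm 40 − 28 = 12. This covers screen failures and attrition together and is not split, so it gives no removal rate. It protects numbers and does not protect against selection.

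**3. Opportunities for removal by arm (arm descriptions in 10.1).**

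| Arm | In-person treatment visits before month 3 |
|---|---|
| PT only | 0 |
| PT + SWT | 3 |
| PT + PBMT | 6 |
| PT + SWT + PBMT | 3 + 3 = 6 |

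The baseline visit is also labelled as the first visit of week 1. If the first device session shares it, the counts of separate visits become 0, 2, 5 and 5. Remote check-ins are counted as visits in PT only, but the text does not say whether missing one triggers removal.

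**4. Total bias of a complete-case contrast.** Let p be the share removed in an arm and d the amount by which removed participants are worse than completers on 3-month VISA-A. Then bias (device minus PT) = p_dev × d_dev − p_PT × d_PT. No p or d is in the documents, so the values below are assumptions.

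| p_dev, p_PT | d_dev, d_PT | Bias (points) |
|---|---|---|
| 0.20, 0.20 | 10, 10 | 0 |
| 0.15, 0.10 | 10, 10 | 0.5 |
| 0.30, 0.10 | 5, 5 | 1.0 |
| 0.30, 0.10 | 10, 10 | 2.0 |
| 0.30, 0.10 | 15, 15 | 3.0 |
| 0.30, 0.10 | 15, 5 | 4.0 (extreme corner) |

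Swapping the arms reverses the sign.

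**5. The part that remote follow-up could avoid.** If a share r of those removed answers remotely, with the same d as those who do not, the bias left in each arm is d × [p − rp/(1 − p + rp)].

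- p = 0.30, r = 0.25: 0.30 − 0.075/0.775 = 0.2032. p = 0.10, r = 0.25: 0.10 − 0.025/0.925 = 0.0730. Difference 0.1303.
- p = 0.30, r = 0.50: 0.30 − 0.15/0.85 = 0.1235. p = 0.10, r = 0.50: 0.10 − 0.05/0.95 = 0.0474. Difference 0.0762.

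| Case | r = 0 | r = 0.25 | r = 0.50 | Avoided |
|---|---|---|---|---|
| 30% vs 10%, d = 10 | 2.0 | 1.30 | 0.76 | 0.70–1.24 |
| 30% vs 10%, d = 15 | 3.0 | 1.95 | 1.14 | 1.05–1.86 |
| 15% vs 10%, d = 10 | 0.5 | 0.35 | 0.22 | 0.15–0.28 |

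If nobody answers, nothing is gained.

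**6. Yardsticks.** The MCID in 11.5 is 6.5 points; the effects in the power statements of 11.2 are 16, 17 and 18 points.

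**The case against.** The recoverable group is narrow. Removal comes only after three attempts, many of those removed will not have replied at all, and a remote questionnaire uses the same contact routes. The 25–50% response is assumed. A removal rate of 30% equals the whole allowance in 11.2, which must also cover screen failures, voluntary withdrawal and mission demands. In the milder case the avoidable bias is under 0.3 points.

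The plan also has mitigations. Entry requires a commitment to 6 months of follow-up (12.5), off-duty participants are paid for the 6-week and 3-month visits (13.2), the 6-week visit may be virtual in every arm, and the multilevel models can use 3- and 6-week scores. The appendices and consent text were not available and might provide for this follow-up. A specific mandatory rule in 10.1 can sit inside a general discretion in 13.6 without contradiction.

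Much of this stands as a limit on size. It does not remove the gap. The rule also covers people who were reached but did not rebook, and someone silent in week 2 may answer at month 3. Commitment at entry and payment may reduce missed visits but do nothing once someone is removed. The multilevel models help only under missing at random and only if earlier scores are kept (13.6 says so just for those who withdraw themselves). They gain little from removals before week 3, and they are not the primary analysis. Whether or not 10.1 and 13.6 strictly conflict, a site reading both cannot tell whether removal is automatic.

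**Conclusion.** The concern holds. Followed as written, section 10.1 gives up primary-outcome data that the study's own remote route could partly collect, and lets attendance help decide who is analysed. Size and direction cannot be derived from the documents. With assumed removal of 10–30% per arm and removed participants 5–15 points worse, equally in both arms, total bias runs from 0 to 3.0 points in either direction, or 4.0 in the extreme corner; in the cases worked, the avoidable part is at most about 1.9 points. That is material beside a 6.5-point MCID and modest beside design effects of 16–18. Differential removal is plausible from the unblinded design and the unequal visit burden, but is not shown. This is a change the sponsor should make; it does not by itself invalidate the design.

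**What to change.** In 10.1 and 13.6, with matching consent wording, state that a randomised participant who misses visits or does not adhere is recorded as a protocol deviation and stays in questionnaire follow-up. The remaining questionnaires, above all the 3-month VISA-A, are requested through the REDCap link or by telephone unless the participant withdraws consent for data collection. The participant is analysed in the randomised arm. The other withdrawal grounds in 13.6 and the pre-randomisation pregnancy withdrawal in 13.3 stay as they are.

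This concerns data collection only. Whether missed study treatment continues is a separate matter, on which the sponsor should reconcile 10.1 with 13.6.

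The cost is protocol and consent wording and a few more reminder contacts; remote capture, reminders (10.1) and a deviation log (16.1) already exist. Section 16.1 leaves the major or minor grading of deviations to the principal investigator and requires major ones to be reported to the IRB within 24 hours, so the grading of missed visits should be settled in advance. Two downsides remain: participants off treatment will dilute the contrast, as intention-to-treat intends, and some people will still be unreachable.
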